Amyloidopathy, Cholinopathy, Dopamine Responsiveness and Freezing of Gait in PD

NCT03647137

05/31/2022

Statistical Analysis Plan

In this proposal, the investigators present data suggesting that L-DOPA refractory freezing of gait (FoG) is associated with comorbid cholinopathy and amyloidopathy in Parkinson's disease.

The investigators propose to test the novel **hypothesis** that comorbid amyloidopathy may be a possible mechanistic factor underlying the poor response of FoG to dopaminergic therapy in advancing PD. In contrast, isolated cholinopathy (without amyloidopathy) would be expected to be associated with preserved dopamine responsiveness of FoG.

For this purpose, the investigators propose to perform detailed motor, including FoG, testing in PD patients "on" and "off" their dopaminergic medications and relate this to dopaminergic 11C- DTBZ, vesicular acetylcholine transporter 18F-FEOBV and amyloid 11C-PIB brain PET imaging in PD subjects with and without FoG.

Our statistical approach is to run a series of hierarchical ordinal logistic regression models, predicting freezing type (L-DOPA responsive, diminished L-DOPA responsiveness, and L-DOPA non-responsive) from dopaminergic (DTBZ), cholinergic (FEOVB), and amyloid (PIB) PET distribution volume ratio (DVR) of the striatum. The null model includes in it striatal DTBZ only. The FEOVB model adds a term for striatal cholinergic innervation. The interaction model, that most directly tests our comorbidity hypothesis adds an interaction term between FEOVB and PIB PET. Goodness of fit for the FEOVB model is compared against the null model, and the interaction model is compared against the FEOVB model.

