Furthermore, based on recent clinical observations that serotonergic drugs, like the popular anti-depressant SSRI drugs, are associated with significantly lower build-up of beta-amyloid plaques in the elderly population, and based on the investigators' subsequent observation of an intriguing inverse relationship between -amyloid plaque deposition and striatal serotonergic terminal in PD, the investigators propose to perform an exploratory sub-study to test an exploratory hypothesis that PD subjects with FoG will exhibit not only higher striatal -amyloid but also lower striatal serotonergic innervation (as determined by 11C-DASB serotonin PET imaging) compared to PD subjects without FoG. Due to a large number of participants taking anti-depressant drugs the number of participants with additional 11C-DASB PET scans was too small to perform a statistical analysis

Protocol Synopsis

Freezing of gait (FoG) becomes more prevalent in advanced Parkinson's disease (PD) and afflicts approximately half of all patients with PD. With disease progression, FoG usually becomes a major contributor to loss of mobility, falls, and decreased quality of life. Elucidation of possible mechanisms underlying dopamine non-responsiveness of gait disturbances in PD, therefore, has high clinical importance.

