The premise of this project is that our preliminary data show that 'uncomplicated' PD—when still in a stage of predominant nigrostriatal dopaminergic denervation—does not have to be a very disabling disease *per se*. As a matter of fact, we found that gait speed in patients with predominant nigrostriatal degeneration is not significantly slower from healthy non-PD control subjects. However, our preliminary data show also that the emergence of non-dopaminergic extra-nigral pathologies in PD may result in significant disability due to FoG. If the association of amyloidopathy and dopamine refractoriness of FoG can be confirmed then this would provide a window for targeted interventions as these at risk-individuals could receive anti-amyloid targeted therapies that might prevent or improve disability in PD. A particular advantage of PD is that the low but symptomatic level of amyloidopathy provides a unique window of opportunity to intervene relatively early in the amyloid cascade. Serotonergic drugs that are already on the market may deserve further study as potential novel anti-amyloid investigational therapeutics, especially when administered very early in the disease course and well before the development of motor complications in PD. Such early and targeted anti-amyloid investigational therapy will critically depend on appropriate biomarker identification of subjects who are at risk of β -amyloid deposition.

The overarching goal of this study is to investigate the relationship between FoG and extranigral pathologies in PD and to test the hypothesis that comorbid amyloidopathy is a mechanistic factor underlying the poor response of FoG to dopaminergic therapy in advancing PD whereas FoG in cholinopathy alone is associated with preserved dopamine responsiveness. To achieve the goals of this project, patients with PD with and without FoG will undergo detailed FoG and gait motor testing in PD patients "on" and "off" their dopaminergic medication. Findings will be related to β -amyloid 11C-PIB, vesicular acetylcholine transporter 18FFEBBV, VMAT2 11C-DTBZ and, in a subset, SERT 11C-DASB brain PET imaging data. Interested subjects may also participate in an additional biomechanical/EMG of FoG and ocular function studies, to be performed on another day.

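### The document itself links antidepressants to amyloid, yet no model or sensitivity analysis accounts for their use, so the PIB main-effect part of the key model comparison could be confounded.

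*Combined protocol and SAP*

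**What the plan says.** All references are to the combined protocol and SAP.

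- **Statistical Analysis Plan, hypothesis.** The trial tests whether "comorbid amyloidopathy may be a possible mechanistic factor underlying the poor response of FoG to dopaminergic therapy".
- **Statistical Analysis Plan, models.** The outcome is freezing type in three ordered levels of L-DOPA response. "The null model includes in it striatal DTBZ only"; the second model adds FEOBV. Then: "The interaction model, that most directly tests our comorbidity hypothesis adds an interaction term between FEOVB and PIB PET". Each model is compared with the one before it. PIB is listed among the predictors, but the text does not say whether it has its own term beside the product, or whether the DVRs are centred.
- **Statistical Analysis Plan, exploratory sub-study.** Serotonergic drugs such as SSRIs "are associated with significantly lower build-up of beta-amyloid plaques in the elderly population". The paragraph closes with the reason why the serotonin PET analysis was not done: "Due to a large number of participants taking anti-depressant drugs the number of participants with additional 11C-DASB PET scans was too small".
- **Protocol Synopsis, premise.** "Serotonergic drugs that are already on the market may deserve further study as potential novel anti-amyloid investigational therapeutics". On the use of the main result: "If the association of amyloidopathy and dopamine refractoriness of FoG can be confirmed then this would provide a window for targeted interventions".

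No section gives a medication covariate, stratification, exclusion or sensitivity analysis. Sample size, significance level, and the class and duration of antidepressant use are not stated.

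**The concern.** The document names a drug exposure that it ties to its key predictor and reports that exposure as common among its own participants. It then deals with the consequence for the DASB scans only, not for the PIB analysis.

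The FEOBV model has no amyloid term. Moving from it to the interaction model therefore tests any PIB main effect and the interaction together. If antidepressant users have lower PIB and also differ in freezing type for some other reason, the PIB part of that comparison could create or hide an amyloid association. The Protocol Synopsis would build targeted anti-amyloid intervention on a confirmed association, so readers should be able to see whether it depends on this exposure.

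**Working it through.** The documents give no sample size, effect size or count of users, so there is no planned figure to reproduce. Every numerical input below is an assumption.

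**1. Which part is exposed.** If PIB has its own term, the last comparison has 2 df: PIB and FEOBV x PIB. If only the product is entered on the raw DVR scale, write f and a for standardised FEOBV and PIB, and m for each mean/SD ratio. The product is then proportional to

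m_A·f + m_F·a + f·a (plus a constant).

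FEOBV is already in the model and absorbs the f part, leaving m_F·a + f·a. With f and a independent, the share of variance due to PIB alone is m_F² / (m_F² + 1). For an assumed m_F = 6 this is 36/37 = 97%; for m_F = 5 it is 25/26 = 96%. An uncentred product is therefore almost entirely a PIB main effect, and the concern applies under either reading of the plan.

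**2. Large-sample bias.** Three-level proportional-odds models, tertile outcome, log-ORs per SD of -0.4 (DTBZ) and -0.5 (FEOBV), use unrelated to FEOBV, true PIB log-OR 0.6 and FEOBV x PIB -0.4. Ratio of unadjusted to adjusted PIB log-OR:

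| Users, PIB deficit in users | drug log-OR -0.8 | drug log-OR +0.8 |
|---|---|---|
| 20%, 0.3 SD (mild) | 1.04 | 0.92 |
| 40%, 0.5 SD (middle) | 1.12 | 0.82 |
| 50%, 0.8 SD (extreme) | 1.20 | 0.745 |

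The largest shift in the FEOBV x PIB coefficient was -0.384 against -0.396, or 0.012/0.396 = 3%.

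**3. False positives of the 2-df comparison.** Same structure, no true PIB or interaction effect, likelihood-ratio test at an assumed 5%, 5,000 runs per cell (Monte Carlo SE near 8%: √(0.08 × 0.92/5000) = 0.4 points). Entries are % rejected, unadjusted vs adjusted for use:

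| Scenario | n | drug -0.8 | drug +0.8 |
|---|---|---|---|
| mild | 40 | 8.1 vs 8.7 | 7.9 vs 8.4 |
| middle | 40 | 9.0 vs 9.2 | 8.7 vs 8.3 |
| extreme | 40 | 10.2 vs 8.8 | 9.2 vs 8.7 |
| mild | 80 | 6.3 vs 6.2 | 6.8 vs 6.6 |
| middle | 80 | 8.1 vs 6.9 | 8.8 vs 7.0 |
| extreme | 80 | 9.5 vs 6.3 | 10.2 vs 6.5 |
| mild | 150 | 5.9 vs 5.8 | 5.9 vs 5.3 |
| middle | 150 | 8.2 vs 5.6 | 7.9 vs 5.5 |
| extreme | 150 | 13.6 vs 6.1 | 13.8 vs 6.1 |

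At n=80 the excess is 1.2-1.8 points in the middle cell and 3.2-3.7 in the extreme cell. Further runs of the same n=80 cells gave 6.8-8.3% vs 5.4-6.8% (middle) and 9.2-12.8% vs 6.5-7.1% (extreme), which widens the extreme excess to about 2-6 points.

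**4. Both links are needed.** A second simulation (n=80, 40% users, 600 runs, SE about 1 point) gave, unadjusted vs adjusted:
- PIB 0.8 SD lower, drug log-odds +1: 12.3 vs 7.0%; log-odds -1: 11.5 vs 6.5%; log-odds 1.5: 18.0 vs 6.8%.
- PIB 0.4 SD lower, log-odds 1: 6.5 vs 6.0%.
- No drug effect on freezing type: 6.2 vs 5.8%.
- No drug effect on PIB: 6.7 vs 5.7%.

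**5. Product only.** Raw product with assumed mean/SD ratios of 6 (FEOBV) and 8 (PIB), extreme cell, n=80: 10.5-11.4% vs 6.1-6.4%. With standardised inputs the product-only test gave 6.1 vs 6.3%.

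**6. Interaction alone.** The Wald test of FEOBV x PIB in the cells of step 3 rejected 4.5-5.7% unadjusted and 4.5-6.1% adjusted. In the second simulation the 1-df likelihood-ratio test against a model with PIB rejected 5.3-7.8% at n=80, with no clear pattern by strength of confounding.

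**The case against.** The strongest objection is that one arm of the confounding is missing from the documents. They link SSRIs to amyloid, but say nothing about antidepressant use and L-DOPA responsiveness of freezing. The sub-study hypothesis concerns serotonergic innervation in patients with and without FoG, which is a different contrast and is not about drug use. The link to amyloid is also thin here: it is reported for SSRIs in elderly people, whereas the trial reports antidepressants in general. All of this stands, and it limits the point to a possibility.

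Second, the interaction, which the plan calls the most direct test of its hypothesis, is nearly untouched. That also stands, given use unrelated to FEOBV. But the planned comparison does not isolate the interaction, because no model with PIB alone comes before it.

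Third, the gain is small unless both links are strong. The mild cell shows nothing, and at n=40 most of the excess over 5% is small-sample inflation that adjustment does not remove.

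Fourth, adjustment is not harmless. If worse freezing itself leads to antidepressant use, the use term could distort the PIB estimate. This is a reason to keep the refit supportive.

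A reader might infer that the amyloid result is confounded, or that the comorbidity test is invalid. The documents do not support either reading: they give no link from use to freezing type, no share of SSRI users and no sample size.

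**Conclusion.** The point holds as a cheap improvement, with medium confidence. The SSRI-amyloid statement, the many antidepressant users and the absence of any analysis accounting for use are all in the text. What could be confounded is the PIB main-effect part of the interaction-versus-FEOBV comparison, whether PIB has its own term or enters through an uncentred product.

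The bias could go in either direction, and it is zero if use affects freezing type only through amyloid or not at all. The n=80 excess of about 1-2 points (middle) and 2-6 points (extreme) rests on assumed prevalence, PIB deficit and drug log-ORs of ±0.8. Stronger links would give more and weaker ones nothing visible. The actual bias in this trial cannot be derived from the documents.

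**What to change.** Keep the planned sequence and make its terms explicit. Suggested SAP text:

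> PIB and FEOBV DVRs will be centred, and PIB enters the interaction model as a main effect together with FEOBV x PIB. A DTBZ + FEOBV + PIB model will be added so that the interaction is also tested on 1 df. Antidepressant use (yes/no; SSRI/SNRI separately where recorded) will be tabulated by freezing type and by striatal PIB. As one supportive analysis, the sequence will be refitted with a binary use term in every model. PIB and FEOBV x PIB log-ORs with 95% CIs, and the model comparisons, will be shown side by side with and without that term. Any material change will be described, with its size, as a limitation on the amyloid interpretation. Persistence of the association will not be taken as proof of mechanism.

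If the models have already been run, label the additions post hoc. The DASB scan count was already known when this text was written, so that may well be the case.

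**Cost.** SAP wording, one table, one added model and one refit. The use term takes 1 df. If use is unrelated to freezing type, the PIB standard error grows by a factor of about √(1 + d²p(1-p)), where p is the proportion of users and d the PIB deficit in SD:
- mild: √(1 + 0.09 × 0.16) = 1.007
- middle: √(1 + 0.25 × 0.24) = 1.030
- extreme: √(1 + 0.64 × 0.25) = 1.077

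In a simulation at n=40 in the extreme cell the factor was 0.352/0.321 = 1.10. With the true effects of step 2 and a drug log-OR of 0, 2-df power in the refit fell by between 0.3 points (81.2 to 80.9%, mild, n=80) and 4.4 points (57.7 to 53.3%, extreme, n=40).

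The refit depends on medication records, which the documents do not confirm for every participant. Yes/no use is a rough proxy for past exposure, so the refit cannot rule confounding out. At about n=40 it is descriptive only.
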